5.4 Duration of Therapy

In the absence of treatment delays due to adverse events, treatment may continue until one of the following criteria applies:

1. Clinically significant progressive disease, or
2. Intercurrent illness that prevents further administration of treatment, or
3. Patient request, or
4. General or specific changes in the patient's condition render the patient unacceptable for further treatment in the judgment of the investigator, or
5. Unacceptable toxicity that in the opinion of the investigator makes it unsafe to continue therapy.

5.4.1 It is planned that up to a total of 24 cycles of therapy will be administered for patients deriving benefit from this regimen. Continuation of therapy for patients completing 24 cycles of therapy may be considered on a case-by-case basis after discussion with the principal investigator.

5.4.2. All patients receiving at least one dose of any of the two drugs will be considered evaluable for toxicity.

5.5 Supportive Care:

Supportive care measures including blood products, infection prophylaxis and growth factors will be administered according to institutional and Leukemia Department guidelines.

Management Algorithms for Treatment of Nivolumab or Ipilimumab Related Adverse Events Immuno-oncology (I-O) agents are associated with AEs

that can differ in severity and duration than AEs caused by other therapeutic classes. Nivolumab and ipilimumab are considered immuno-oncology agent in this protocol. Early recognition and management of AEs associated with immuno-oncology agents such as nivolumab and/or ipilimumab may mitigate severe toxicity. Nivolumab and ipilimumab have a known safety profile however, a general principle is that differential diagnoses should be diligently evaluated according to standard medical practice. Non- inflammatory etiologies should be considered and appropriately treated. Corticosteroids are a primary therapy for immuno-oncology drug-related adverse events, and nivolumab or ipilimumab no exception. The oral equivalent of the recommended IV doses may be considered for ambulatory patients with low-grade toxicities. The lower bioavailability of oral corticosteroids should be taken into account when switching to the equivalent dose of oral corticosteroids.

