9.1 Discontinuation Criteria for Individual Patients

9.1.1 Patient Withdrawal

Patients may voluntarily withdraw consent to participate in the clinical study at any time and without giving any reason. Their withdrawal will not jeopardize their relationship with their healthcare providers or affect their future care. Patients may also choose to withdraw from study treatment, but agree to remain in the study for

follow-up procedures.

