9.1.4 Follow-Up at Treatment Discontinuation or Early Withdrawal

Patients who discontinue treatment for any reason should complete end-of-treatment procedures when possible. End of treatment procedures will include a physical examination, CBC with differential and platelets and a limited chemistry profile (total bilirubin, serum creatinine, SGPT or SGOT). A bone marrow aspiration may be recommended only if non-response or progressive disease cannot be unequivocally diagnosed from peripheral blood. Although treatment will be discontinued at that time, all patients who do not withdraw consent for follow-up, die, or become lost to follow-up, will remain on study for follow-up evaluations. Subject will be followed for toxicity for at least 30 days after the last protocol treatment. The 30-day follow-up visit (+ or - 3 days) will be scheduled as a clinic visits for clinical evaluation and physical examinations. If the patient cannot make it to the MDACC clinic for this visit, the required follow up treatment procedures may be done with a local physician and the records forwarded to MDACC. The research nurse will contact the patient by telephone and get a verbal assessment of the patient's condition. The phone conversation will then be documented in the patient's charts.

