11.2 Sample Size

Arm 1:***Part a. Lead-in phase***

The primary objective of the lead-in phase is to determine the safety of nivolumab in combination with 5-azacytidine in patients with refractory/ relapsed AML. Up to 30 patients will be accrued into the lead-in part of the study.

Part b. Expansion phase

- A. Up to 70 patients (including 6 patients treated at the MTD from the lead-in part) with relapsed/refractory AML will be recruited for the Arm 1 Salvage cohort .
- B. Up to 40 newly diagnosed older AML patients (age ≥ 65) will be recruited for the Arm 1 Frontline older cohort .

Arm 2:**Part a. Lead-in phase**

The primary objective of the lead-in phase is to determine the safety of nivolumab with ipilimumab in combination with 5-azacytidine in patients with refractory/ relapsed AML. Up to 24 patients will be accrued into the lead-in part of the study.

Part b. Expansion phase

- A. Up to 54 patients (including 6 patients treated at the MTD from the lead-in part) with relapsed/refractory AML will be recruited for the Arm 2 Salvage cohort.
- B. Up to 30 newly diagnosed older AML patients (age ≥ 65) will be recruited for the Arm 2 Frontline older cohort.

The efficacy of the combination will be measured by the overall response rate (ORR), defined as CR (complete remission) + CR_p (complete remission with incomplete platelet recovery) + CR_i (complete remission with incomplete count recovery) + PR (partial response) + marrow clearance of blasts + hematologic improvement (HI) in platelets, hemoglobin, or ANC within 3 months of treatment initiation among adult patients with refractory/ relapsed AML AND newly diagnosed older patients with AML. ORR and toxicity will be monitored simultaneously using the Bayesian approach of Thall, Simon, Estey (1995, 1996) and the extension by Thall and Sung (1998).

Arm 3:**Part a. Lead-in phase**

The primary objective of the lead-in phase is to determine the safety of nivolumab with 5-azacytidine and venetoclax in patients with refractory/ relapsed AML. A total of 18 patients (3 dose levels with a maximum of 6 patients at each dose level) will be accrued into the lead-in part of the study.

Part b. Expansion phase

- A. A total of 30 patients (excluding 6 patients treated at the MTD from the lead-in part) with relapsed/refractory AML will be recruited for the Arm 3Salvage cohort.
- B. A total of 30 newly diagnosed older AML patients (age ≥ 65) will be recruited for the Arm 3 Frontline older cohort.

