Once safety of the MTD has been established, any patients still on study at a dose lower than MTD can be dose escalated up to MTD. Patients treated in the lead-in phase at MTD

will be included in the Phase II portion of the study.

The efficacy of the combination will be measured by the overall response rate (ORR), defined as CR (complete remission) + CRp (complete remission with incomplete platelet recovery) + CRi (complete remission with incomplete count recovery) + MLFS within 6 months of treatment initiation among adult patients with refractory/ relapsed AML AND newly diagnosed older patients with AML. ORR and toxicity will be monitored simultaneously using the Bayesian approach of Thall, Simon, Estey (1995, 1996) and the extension by Thall and Sung (1998).

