| # patients with toxicities | 3 | 5-6 | 6-9 | 7-12 | 8-15 | 9-18 | 11-21 |
| # patients evaluated | 24 | 27 | 30 | 33 | 36 | 39 | 42 |
| # patients with toxicities | 12-24 | 13-27 | 14-30 | 15-33 | 16-36 | 17-39 | 18-42 |
| # patients evaluated | 45 | 48 | 61 | 54 | 57 | 60 | 63 |
| # patients with toxicities | 19-45 | 20-48 | 22-51 | 23-54 | 24-57 | 25-60 | 26-63 |
| # patients evaluated | 66 | 70 | | | | | |
| # patients with toxicities | 27-66 | Always stop with this many patients | | | | | |

Monitoring the ORR rate, based on the above assumptions and monitoring conditions is found in Table 10. **For example, accrual will cease if no patient experience an overall response within 3 months of initiation of therapy in the first 9 patients treated.**

| Table 10. Stop accrual if the number with overall response is less than or equal to indicated (i.e., # patients with overall response) among the number of patients evaluated | | | | | | | |
|---|------------------------------------|-------|-------|-------|-------|-------|-------------------------------------|
| # patients evaluated | 3-6 | 9-12 | 15-18 | 21-24 | 27-30 | 33 | 36-39 |
| # patients with overall response | Never stop with this many patients | 0 | 1 | 2 | 3 | 4 | 5 |
| # patients evaluated | 42 | 45-48 | 51 | 54-57 | 60 | 63-66 | 70 |
| # patients with overall response | 6 | 7 | 8 | 9 | 10 | 11 | Always stop with this many patients |

Multi Lean Desktop (version 2.1.0) was used to generate the toxicity and futility stopping boundaries and the OC table (Table 11). In order to utilize the software for the design, a 15% constant rate and beta(0.3, 1.7) priors were assumed for the standard treatment response distribution and experimental treatment response prior distribution, respectively. In addition, a 30% toxicity constant rate and beta (0.6, 1.4) priors were assumed for the standard treatment toxicity constant rate and experimental treatment toxicity prior distribution, respectively.

The probability of stopping the study early if the true ORR of the combination treatment was 30% and the true toxicity rate was 30% was 24.7%. Probabilities of stopping early for high true toxicity rates (i.e., 50%) were 97.5% when the true ORR was 30% and 99.6% when true ORR rate was 15%.

Table 11. Operating characteristics for simultaneous monitoring response and toxicity rates for patients treated with combination treatment

| True Toxicity Rate | True ORR | Prob(stop the trial early) |

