| | 0.90 | 0.1194 |
| 0.40 | 0.60 | 0.8740 |
| | 0.70 | 0.6569 |
| | 0.80 | 0.4589 |
| | 0.85 | 0.4109 |
| | 0.90 | 0.3907 |
| 0.50 | 0.60 | 0.9465 |
| | 0.70 | 0.8543 |
| | 0.80 | 0.7702 |

| Nivolumab and azacytidine | | |
|---------------------------|---------------|------------------|
| True Toxicity Rate | True ORR Rate | PROB(Stop Early) |
| | 0.85 | 0.7498 |
| | 0.90 | 0.7412 |

The Investigator is responsible for completing an efficacy/safety summary report, and submitting it to the IND Office Medical Affairs and Safety Group, for review and approval. This should be submitted as follows:

Lead-in Phase:

Every 6 evaluable patients complete cycle 1 of study therapy before advancing/changing dose levels.

Expansion Phase:

After the first 5 evaluable patients per cohort, complete 3 months of study treatment, and every 5 evaluable patients per cohort, thereafter.

A copy of the cohort summary should be placed in the Investigator's Regulatory Binder under "sponsor correspondence".

Statistical Analysis Plan

All patients who received any dose of the study agent will be included in the analysis for efficacy and safety. Demographic/clinical characteristics (including duration of response) and safety data of the patients will be summarized using descriptive statistics such as mean, standard deviation, median and range. For the primary efficacy analysis, we will estimate the ORR for the combination treatment, along with the 95% confidence interval. Patients who drop out of the study before completing all the cycles will be treated as "failures" for the primary analysis. Overall response rate (ORR) during the study period will also be presented with the 95% confidence interval. The association between ORR and patient's clinical characteristics will be examined by Wilcoxon's rank sum test or Fisher's exact test, as appropriate. Toxicity type, severity and attribution will be summarized for each patient using frequency tables.

The distribution of time-to-event endpoints (DFS and OS) including overall survival and progression free survival will be estimated using the method of Kaplan and Meier.

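### The primary response-rate analysis fails patients who drop out before finishing all cycles, even if they responded within the 3- or 6-month window that defines the endpoint

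*Combined protocol and SAP*

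**What the plan says.** Section 11.2 gives ORR a fixed time window. For Arms 1 and 2 a qualifying response must occur "within 3 months of treatment initiation among adult patients"; for Arm 3, "within 6 months of treatment initiation among adult patients".

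The Statistical Analysis Plan text at the end of Section 11.3 puts every treated patient in the efficacy analysis and takes ORR with a 95% confidence interval as the primary estimate. It then adds: "Patients who drop out of the study before completing all the cycles will be treated as" failures for that analysis. A second estimate follows: "Overall response rate (ORR) during the study period will also be presented with the 95% confidence interval".

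The number of cycles appears only in Section 5.4.1: "It is planned that up to a total of 24 cycles of therapy will be administered for patients deriving benefit from this regimen".

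On leaving treatment versus leaving the study, Section 9.1.1 says: "Patients may also choose to withdraw from study treatment, but agree to remain in the study for" follow-up. Section 9.1.4 says that after treatment stops, "all patients who do not withdraw consent for follow-up, die, or become lost to follow-up, will remain on study for follow-up evaluations".

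The interim response rules in Section 11.3 for Arms 1 and 2 use the 3-month window and state no drop-out condition. For the Arm 1 salvage cohort, for example, "accrual will cease if no patient experience an overall response within 3 months of initiation of therapy in the first 9 patients treated".

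**The concern.** Whether a patient met the ORR definition is settled by month 3 or month 6. The failure rule depends on a different and possibly much later event. A patient with a documented complete remission at month 2 who withdraws consent at month 9 meets the Section 11.2 definition, yet is a failure under the SAP sentence.

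Both terms that trigger the rule are open to interpretation. Section 5.4.1 sets a maximum number of cycles, not a course that every patient is meant to finish. The protocol also uses off-study language loosely. Sections 9.1.1 and 9.1.4 separate stopping treatment from leaving the study. Tables 6A to 6C remove patients from the study for repeated toxicity, and the DLT text in Section 5.2.1.4 allows some patients who have come off study to go on receiving protocol therapy. Section 9.1.4 lists death among the reasons for not remaining on study, and the SAP does not say whether a responder who later dies has dropped out.

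Two analysts could therefore report different primary ORRs from the same data. A responder counted at an interim look could also become a failure in the final estimate, making an active regimen look closer to its historical rate.

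**Working it through.** **1. The windows against the cycle count.** Section 5.2.2 sets a cycle at 28 days, and a month is taken as 30.44 days.

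- Arms 1 and 2: 3 × 30.44 / 28 = 3.3 cycles.
- Arm 3: 6 × 30.44 / 28 = 6.5 cycles.
- Planned maximum: 24 × 28 = 672 days; 672 / 30.44 = 22.1 months.

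On the longest reading, a responder stays exposed to reclassification for about 19 months after the Arm 1 and 2 window closes (22.1 − 3) and about 16 months after the Arm 3 window closes (22.1 − 6).

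**2. The design figures contain no drop-out rule.** I recomputed the probability of early stopping by exact binomial recursion over the printed boundaries, with response and toxicity independent and each response counted at the true ORR. At true toxicity 0.30:

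| Cohort | True ORR | Plan | Recomputed |
|---|---|---|---|
| Arm 3 frontline | 0.80 | 0.2180 | 0.2180 |
| Arm 3 salvage | 0.60 | 0.2393 | 0.2393 |
| Arm 2 salvage | 0.30 | 0.1694 | 0.1694 |

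The agreement shows that the operating characteristics treat every response as a response, with no later reclassification.

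**3. Effect on the reported rate.** Let q be the share of in-window responders who later drop out in the SAP's sense. Then

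reported ORR = true ORR × (1 − q).

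The documents do not give q, so 10% and 25% are assumptions. The true rates are the plan's target or assumed values: 30% (Arm 1 and 2 salvage), 40% (Arm 1 and 2 frontline), 60% (Arm 3 salvage) and 80% (Arm 3 frontline).

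| q | 30% | 40% | 60% | 80% |
|---|---|---|---|---|
| 10% | 27% | 36% | 54% | 72% |
| 25% | 22.5% | 30% | 45% | 60% |

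The q at which the reported rate falls to the historical rate used in the design is 1 − historical / true:

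- Arm 3 frontline: 1 − 0.60/0.80 = 25%.
- Arm 1 and 2 frontline: 1 − 0.25/0.40 = 37.5%.
- Arm 1 and 2 salvage: 1 − 0.15/0.30 = 50%.
- Arm 3 salvage: 1 − 0.25/0.60 = 58%.

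**4. In patients, Arm 3 frontline (N = 30).** The SAP names no interval method; Clopper-Pearson 95% limits are assumed.

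| Responders later dropping out | Counted | ORR | 95% CI |
|---|---|---|---|
| 0 | 24/30 | 80.0% | 61.4–92.3% |
| 1 | 23/30 | 76.7% | 57.7–90.1% |
| 6 | 18/30 | 60.0% | 40.6–77.3% |

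The SAP attaches no decision to these limits, so they show sensitivity only.

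**The case against.** The best defence is that the sentence is an ordinary missing-data convention. It comes shortly after the statement that all treated patients are analysed, and may mean only that early leavers stay in the denominator as non-responders. The 24 cycles are a ceiling for patients who benefit, and nothing links them to ORR. Section 9.1.4 keeps patients who stop treatment on study unless they withdraw consent, die or are lost, so drop-out may be rare and 25% may be too high. Table 1 in Section 2.3 D tabulates best response for the closed Arm 1 salvage cohort as 23 of 70 and mentions no reclassification. ORR over the study period is also reported, and no stopping boundary or decision rule uses the final interval. The one-patient example depends on the 60% reference: Section 11.3 also cites a historical 66%, and the lower limit for 24/30 is already below that.

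Most of this stands as a limit on size. The drop-out shares are assumed, and the example is only illustrative. None of it repairs the rule. Treating drop-outs as failures is sound where no outcome was seen in the window, but this sentence also reaches patients whose response was documented. Even on the narrowest reading (withdrawal of consent or loss to follow-up), such a patient is misclassified. The study-period estimate has no stated window and is not primary. Table 1 may show what the team does in practice, but it is not the SAP analysis.

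**Conclusion.** The rule is wrong as written and should be fixed. The primary ORR under the SAP sentence is not the quantity Section 11.2 defines whenever an in-window responder later drops out, and the result depends on two undefined terms.

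The size is unknown. On the narrow reading few patients would be affected. If deaths also count as drop-out, many could be: Section 2.3 D reports median overall survival in the salvage setting of 6.4 months (Aza+Nivo) and 10.5 months (Aza+Ipi+Nivo), against about 22 months for 24 cycles. Those medians cover all patients rather than responders, so they indicate direction only. Under the assumed 10% to 25%, a true 80% is reported as 72% to 60%.

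The error can only lower the estimate. It cannot create a false claim of activity, and the interim boundaries as printed are unaffected.

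**What to change.** Replace the SAP sentence with:

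> Patients without a documented qualifying response within 3 months (Arms 1 and 2) or 6 months (Arm 3) of starting treatment, including those who die, drop out or are not assessed in that window, are non-responders. A response documented within the window counts regardless of later discontinuation or withdrawal.

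This still counts unassessed patients as non-responders, matches the Section 11.2 definition and the interim counts, and removes any need to define how many cycles make up the full course. The study-period ORR can stay as a supplementary figure. The cost is one SAP passage, changed through a routine protocol amendment, with no new data, patients or boundaries.

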12.0 PROTOCOL ADMINISTRATION

This study will be monitored for compliance by the IND Office.

Protocol amendments

Changes to the protocol will be made only when protocol amendments have been signed by the principal investigator and approved by the sponsor and the IRB of the study center.

Archival of data

All patient data (including source data) generated in connection with this study will be kept in the archives of the MDACC for at least 15 years after the study has been completed. All data will be available for inspection by company representatives of the Medical Department and by regulatory authorities.

14.0 APPENDICES

Appendix A: Prioritization List

Appendix B: Protocol Checklist

Appendix C: CTCAE version 4.0

Appendix D: Leukemia specific AE recording and reporting guidelines

Appendix E: Generic-Nivolumab Drug Information

Appendix F: Generic-Vidaza Drug Information

Appendix G: Management algorithms for immuno-oncology drug-related adverse events

Appendix H: Outside Physician Form

Appendix I: DOSING PROCEDURE MANUAL for Lirilumab and Nivolumab Version 2.0

Appendix J: Ipilimumab IB

Appendix K: Nivolumab and Ipilimumab product information
